## **6. DATA SETS ANALYZED (STUDY POPULATIONS)**

Study populations are defined as follows:

### **6.1. Safety Set**

The Safety Set includes all patients who receive at least 1 dose of ALXN1007. This set will be used to summarize demographics, baseline characteristics, medical history, prior and concomitant medications, adverse events, laboratory results, vital signs and ECG.

### **6.2. Modified Safety Set**

The modified Safety Set is defined as all patients who receive at least 1 dose of ALXN1007 and for whom GI GVHD is confirmed through biopsy. The modified safety set defined in the protocol has the identical definition as the modified full analysis set defined below. Hence this set will not be used for any pre-specified analyses covered by this statistical analysis plan.

### **6.3. Modified Full Analysis Set (mFAS)**

The mFAS will include all patients who receive at least 1 dose of ALXN1007 and for whom GI GVHD is confirmed through biopsy. This analysis set will be used for efficacy analysis.

### **6.4. Per Protocol Set (PP)**

The Per-Protocol (PP) Set is a subset of the mFAS population, excluding patients with major protocol deviations. This population may be used to summarize efficacy. Protocol deviations will be classified in the following categories:

- Did not fulfill eligibility criteria
- Met discontinuation criteria but continued IP treatment
- Received incorrect IP/dose
- Received prohibited concomitant medication
- Protocol-required procedure not adhered to
- Other

The PP analysis set will be identified prior to database lock.

Note: For abbreviated CSR, Per Protocol Set will not be derived.

### **6.5. PK/PD Analysis Set**

PK/PD analyses will be performed on the PK/PD Analysis Set. The PK/PD Analysis Set includes all patients who receive at least 1 dose of ALXN1007 and who have evaluable PK and PD data. Refer to PK/PD analysis plan for details.

Note: For abbreviated CSR, PK analysis Set will not be derived.

## **7. STATISTICAL ANALYSIS**

All statistical calculations will be performed using SAS, unless otherwise specified. All data will be presented in the form of listings sorted by treatment group (cohort) and patient ID. Tabular summaries will be presented based on the following grouping: 10mg/kg once weekly, 20mg/kg once weekly, 20mg/kg twice weekly and overall (all three treatment groups combined).

For continuous variables, summary statistics will include sample size, mean, standard deviation, median, minimum, and maximum values. Frequencies and percentages will be calculated for categorical variables. Graphical displays will be produced, as mentioned in this SAP.

### **7.1. Study Subjects**

#### **7.1.1. Disposition of Subjects**

Following summaries will be tabulated:

- Number of patients screened and reasons for screen failure
- Number of patients treated
- Number of patients in safety set and number of patients excluded from this set along with reasons
- Number of patients in modified full analysis set and number of patients excluded from this set along with reasons (Note: For abbreviated CSR, Per Protocol Set will not be derived.)
- Number of patients in per protocol set and number of patients excluded from this set along with reasons
- Number of patients completed and discontinued along with reasons for discontinuation during treatment period, follow-up period as well as overall study
- Survival status at Day 360

#### **7.1.2. Protocol Deviations**

All the protocol deviations will be listed. Number and percentage of patients not meeting inclusion/exclusion criteria will be tabulated for safety set.

Note: tabular summary will not be presented for protocol deviations; by-patient listing will be produced.

#### **7.1.3. Demographics, Disease Characteristics and Medical History**

All demographic and medical history information will be summarized using Safety set.

##### **7.1.3.1. Demographics**

The following demographic variables will be summarized:

- Age (Years)

- Sex
- Race
- Ethnicity
- Weight (kg)
- Height (cm)

### **7.1.3.2. Disease Characteristics**

Following disease characteristics will be tabulated:

#### **7.1.3.2.1. Transplant history**

- Donor type (matched related, matched unrelated, mismatched, other) (n, %)
- Graft source (Bone marrow, peripheral blood, umbilical cord) (n, %)
- Transplant indication (acute myeloid leukemia, mantle cell lymphoma etc.) (n, %); these indications will be identified by review of medical history.

#### **7.1.3.2.2. Endoscopy, Biopsy and GI-GVHD confirmation**

- GI-GVHD onset day categories post-transplant at enrollment (<10, 10-19, 20-29, 30-39, 40-49, 50-59, ≥60) (n, %)
- Confirmation of GI-GVHD through upper GI tract biopsy (yes, no)
- Confirmation of GI-GVHD through lower GI tract biopsy (yes, no)

#### **7.1.3.2.3. Baseline Staging Information, Extent of Rash, Stool Volume**

- Staging score (0, 1, 2, 3 and 4) for each organ (skin, lower GI tract and liver) (n, %)

### **7.1.3.3. Medical History**

Medical history will be tabulated by number (%) of patients in the Safety Set for each system organ class and preferred term.

Note: For abbreviated CSR, no tabular summary will be provided for medical history, however a by-patient listing will be produced.

### **7.1.4. Prior and Concomitant Medications / Therapies**

Prior medications are defined as medications taken or therapies received by patients prior to the first dose of ALXN1007. Concomitant medications are defined as medications taken or therapies received by patients during the study after first dose of ALXN1007. Medications will be coded using the World Health Organization Drug Dictionary version. Summaries will be performed on the Safety set. A medication will be considered conservatively both prior and concomitant if partial start or stop dates are recorded such that its designation as a prior and/or concomitant medication could not be determined with certainty.

The number (%) of patients taking prior and concomitant medications will be summarized based on the World Health Organization Anatomical Therapeutic Chemical (WHO ATC) Level 1 and generic name. In addition, by-patient listings will be provided for the following:

- Prior investigational agents
- Secondary therapies (during the study)

## **7.2. Efficacy Analyses**

Efficacy analyses will be performed on the modified Full Analysis Set (mFAS). For efficacy, Baseline is defined as the first available assessment prior to first dose of ALXN1007, this value is supposed to be representative of value at diagnosis of GI-GVHD.

### **7.2.1. Primary Efficacy Analysis**

Overall GVHD response rate along with 95% confidence intervals (CIs) will be calculated at Day 28. The confidence interval will be calculated using Clopper-Pearson exact method.

#### **7.2.1.1. Handling of Dropouts or Missing Data**

- Imputations will be performed up to Day 180 visit (maximum visit for stage data)
- If a patient has been administered with secondary therapy or died before the next missing visit, all subsequent missing values will be imputed as NR (non-responder), otherwise, last non-missing response will be carried forward.

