^{*} Screening period for the study will be initiated after informed consent form signing (ie, subject enrollment). Acute GI GVHD staging at the time of diagnosis (that can be made up to 7 days prior to the first ALXN1007 dose) will be captured and used for comparison to post-Baseline GVHD staging to assess treatment response.

^{**} With approval of Amendment 6, Cohort 2 (20 mg/kg QW for 8 weeks) will be added to the study. An additional cohort (Cohort 3, 20 mg/kg twice weekly for 8 weeks), is planned after DMC review of safety and tolerability data at Day 28 on the first 3 patients in Cohort 2. At the discretion of the Sponsor, and in consultation with the DMC, other dosing cohorts (not to exceed a total dose of 40 mg/kg per week for 8 weeks) may also be explored based on cumulating safety and tolerability data as well as any PK/PD data that may be available.

^{***} Follow-up period for the study consists of study visits at Weeks 12 (Day 86) and 26 (Day 180), with telephone contact at Week 52 (Day 360) for survival status only.

Table 3: Schedule of Events for Subjects on a Once Weekly ALXN1007 Dosing Schedule

Procedures and Evaluations	Screening	Treatment (± 2 days)										Follow-up (± 15 days, except for ET)			
Weeks		0	1	2	3	4	5	6	7	8	12	26		52	
Days	-3 to -1	Baseline	7	14	21	28	35	42	49	56	86	180	ET	360	
Informed Consent	X														
Eligibility - Inclusion/Exclusion Criteria	X	X^1													
Medical History, Demographics	X														
ALXN1007 Administration ²		X	X	X	X	X	X	X	X						
Acute GVHD Staging ³	X	X	X	X	X	X	X	X	X	X	X	X	X		
Antibiotic Prophylaxis Against Meningococcal Infection ⁴	X	X	X	X	X	X	X	X	X	X	X ⁴		X ⁴		
Physical Exam ⁵	X					X				X		X	X		
ECG		X^6				X^6				X		X	X		
Vital Signs ⁷	X	X	X	X	X	X	X	X	X	X	X	X	X		
Weight	X	X	X	X	X	X	X	X	X	X	X	X	X		
Stool Clostridium difficile Testing (Local lab)	X														
CSA, Tacrolimus, and/or Sirolimus Levels (if needed) ⁸		X	X		X		Х		X				X		
CMV-PCR		X	X	X	X	X	X	X	X	X			X		
Routine Laboratory Test ⁹	X	X	X	X	X	X	X	X	X	X	X	X	X		
Creatinine Clearance (local lab)	X														
ANC (local lab)	X														
Endoscopy of Upper and/or Lower GI Tract / Biopsy ¹	X														
CPK, Thyroid Function Tests (Central lab)		X	X			X				X	X	X	X		

Table 3: Schedule of Events (Continued)

Procedures and Evaluations	Screening		Treatment (± 2 days)							Follow-up (± 15 days, except for ET)				
Days	-3 to -1	to -1 Baseline 7 14 21 28 35 42 49 56	56	86	180	ET	360							

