13.7.1. Overall Acute GVHD Response Rate

The proportion of subjects with overall response will be summarized by visit and 95% CIs will be calculated. Subjects who discontinue from the study early will be imputed as having no response.

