#### 5.1.1. Primary Endpoint(s)

The primary efficacy endpoint is the overall acute GVHD response at Day 28. The overall acute GVHD response is defined as improvement from Baseline in any organ (skin, lower GI tract and liver) by at least 1 stage, without progression in any other organ and with no additional therapy being administered. Baseline will be defined as the stage value determined at the diagnosis i.e. the first value recorded prior to 1st ALXN1007 infusion. At every visit, patients will be graded according to the Modified Keystone Grading Schema displayed in **Table 2**.

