### **Imputation technique for missing acute GI-GVHD and all organ-GVHD response**

- There could be two types of missing data
  - Missing data at intermediate visits (for example, patient may miss Day 28 visit but still has data on Day 21 and 35).
  - Missing data due to discontinuation or deaths.
- Imputations will be performed up to Day 180 visit (maximum visit for stage data)
- For missing visits due to death, all subsequent visits will be imputed as “progression” (irrespective of secondary therapy); note, the protocol defined visit windows can be either  $\pm 2$  or  $\pm 15$  days depending on whether they fall in the treatment-period vs. follow-up period. However, the analysis windows are wider than protocol defined visit windows; if death occurs within a pre-specified analysis window for a particular visit (even if the target day for that visit is less than the day of death), missing values will be considered as ‘progression’.
  - Example: non-missing responses on Day 7, secondary therapy starting on Day 9, death on day 10, Day 14 onward – impute as progression.
- If all post-baseline responses are missing due to an early death, then missing responses will be imputed as “progression”.
- For other missing visits, following imputation rules will be implemented:
  - If the previous observed response is “Progression”, then subsequent missing visits will be imputed as “Progression” irrespective of secondary therapy
  - If response is not “progression” at the previous visit and a patient has been administered with secondary therapy since then, all subsequent missing visits will be imputed as NR
    - Example: Day 14 is CR, Day 28 and Day 35 visits are missing
      - If no secondary therapy flag before Day 28, then Day 28 response will be imputed as CR
      - If secondary therapy administered before Day 28, both Day 28 and 35 missing responses will be imputed as NR
  - Otherwise, carry forward the last non-missing response. Only post-baseline responses are carried forward. If first post-baseline response is missing and the patient did not die, no response can be carried forward.

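### The primary endpoint's missing-data rule has no analysis-window clause for death, so an earlier responder who misses Day 28 and dies just after it can count as a primary responder but as progression in the all-organ table

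*SAP*

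**What the plan says.** SAP 7.2.1.1 gives the primary endpoint its own missing-data rule. A missing value becomes non-response after secondary therapy, or when the patient "died before the next missing visit, all subsequent missing values will be imputed as NR (non-responder), otherwise, last non-missing response will be carried forward". The rule does not mention analysis windows, and it does not say whether a missing visit is placed at its target day or at the end of its window.

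SAP 7.2.2.1 has a separate block of rules headed "Imputation technique for missing acute GI-GVHD and all organ-GVHD response". It notes that "the analysis windows are wider than protocol defined visit windows". It then sets the missing value to progression "if death occurs within a pre-specified analysis window for a particular visit (even if the target day for that visit is less than" (here the comparison is with the day of death). The primary endpoint is not named in that heading, and 7.2.1.1 does not refer to it. The windows are described as pre-specified, but neither document gives their limits.

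The protocol's simpler rule for the primary (Section 13.7.1) was "Subjects who discontinue from the study early will be imputed as having no response". SAP 4.1 states that this imputation rule has been changed for all three response endpoints, so it no longer covers the case.

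**The concern.** The primary endpoint and all-organ CR plus PR describe the same clinical state, yet they have different rules for death. The SAP's authors saw the case of a patient who dies shortly after a target day with that visit missing. They wrote a clause for it, but only in the section on the other two response endpoints.

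Take a subject with PR at Day 21, no secondary therapy, no Day 28 staging and death on Day 30. With the primary rule read by target day, death did not precede Day 28, so PR is carried forward and the subject is a Day 28 responder. The all-organ table shows the same subject as progression at Day 28. At stake are a possible upward error in the primary rate and two tables in one report that do not reconcile.

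**Working it through.** **1. The two endpoints are the same state.** SAP 5.1.1 says "The overall acute GVHD response is defined as improvement from Baseline in any organ" by at least one stage, with no progression in another organ and no additional therapy. In SAP 5.1.2.2, all-organ PR is improvement in at least one organ with no deterioration in another, CR is stage 0 in every organ, and secondary therapy is assigned to NR first. Inclusion criterion 2 requires lower GI Stage 1 to 4 at diagnosis, so every CR is also an improvement. Taking additional therapy to mean secondary therapy as defined in SAP 5.1, primary response equals all-organ CR + PR on observed data.

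**2. The two rules by day of death.** The subject's last response is PR, Day 28 is missing and there was no secondary therapy. The primary rule is read by target day.

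| Day of death | Primary (7.2.1.1) | All-organ (7.2.2.1) | Same responder status? |
|---|---|---|---|
| 25 to 27 | NR | Progression | Yes, both non-response |
| 28 to 30 (half-window 2 days) | PR carried forward | Progression | No |
| 31 (half-window at least 3 days) | PR carried forward | Progression | No |

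At the next visit (Day 35) death has come first under either rule, so the conflict is confined to the visit whose window contains the death.

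**3. How many subjects.** The plan states no figure to reproduce. Inputs:
- Day 56 mortality m: 20% anticipated and 40% unacceptable (protocol 6.5.4).
- Maximum N: 36 (protocol 6.2).
- Half-window w: not given. Assumed 2 to 3.5 days. The lower end is the weekly-schedule visit window, which the SAP says its analysis windows exceed. The upper end is the widest that does not overlap the neighbouring weekly visits.
- Hazard: assumed constant.
- Earlier response: assumed 50%, for scale only. Protocol 4.4 says corticosteroids help about half of patients.

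Formula: h = −ln(1 − m)/56, and P(death in the late half-window) = exp(−28h) − exp(−(28 + w)h).

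| m | w (days) | P | × 36 | × 0.5 |
|---|---|---|---|---|
| 20% | 2 | 0.0071 | 0.26 | 0.13 |
| 20% | 3 | 0.0106 | 0.38 | 0.19 |
| 20% | 3.5 | 0.0124 | 0.45 | 0.22 |
| 40% | 2 | 0.0140 | 0.50 | 0.25 |
| 40% | 3 | 0.0209 | 0.75 | 0.38 |
| 40% | 3.5 | 0.0243 | 0.88 | 0.44 |

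Given the hazard and response assumptions, the last column is an upper bound. It supposes that every such subject missed Day 28 and that none had secondary therapy.

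**4. What one subject does.** 1/36 = 2.8 points, 1/30 = 3.3, 1/18 = 5.6 and 1/6 = 16.7. At n = 18, correcting one such subject moves 10/18 = 55.6% (Clopper-Pearson 95% CI 30.8 to 78.5) to 9/18 = 50.0% (26.0 to 74.0).

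**5. Whether anything else catches it.** The sensitivity analysis in SAP 7.2.1.5 uses observed data only. The subject leaves the denominator (9/17 = 52.9% in the example) and is not counted as a failure. Treatment failure, which includes death, is not analysed for the abbreviated report (SAP 5.1.2.4). The all-organ response carries no such exclusion, so both tables would be produced.

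**The case against.** The strongest reply is that 7.2.1.1 is unclear rather than lenient. Because the SAP's analysis windows are wider than the visit windows, a visit is arguably missing only once its window has closed without an assessment. On that reading a Day 30 death precedes the missing visit, the primary is NR and the conflict disappears. This is a fair reading, but the SAP does not state it, and the explicit window clause stands under a heading that leaves the primary out. A programmer could code either.

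The reply is also right that the case is narrow. Staging is scheduled weekly, any staging inside the window removes the need to impute, and a patient dying of GVHD may well have had secondary therapy, which is NR in any case. Little rides on the result: there is no hypothesis test, the study ended early, observed and imputed rates are both shown, staging is listed by patient and survival is reported separately. Those listings would make such a case visible, but they would not correct the primary rate.

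A reader might infer two stronger things. One is that every death in the Day 28 window produces the conflict. It does not: before the target day both rules give non-response, and only the labels differ. The other is that the SAP deliberately gives the primary a more lenient death rule. The text shows an omission and an undefined phrase, and does not establish intent.

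**Conclusion.** The point holds in a narrow form and is minor. Read by target day, 7.2.1.1 lets a subject be a Day 28 primary responder and an all-organ progression at once. This requires an earlier CR or PR, no secondary therapy, no Day 28 assessment, and death on or after target Day 28 but within its analysis window. The error runs one way: it can only raise the primary rate.

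The expected size at the anticipated 20% mortality is at most about 0.13 to 0.22 of 36 subjects, or roughly 0.4 to 0.6 points (0.13/36 and 0.22/36). At 40% mortality it is 0.25 to 0.44 subjects. These figures rest on the assumed constant hazard, half-window and 50% earlier response. The most likely outcome is that no subject is affected. The point is still worth making because results are tabulated by cohort, where a single subject in a group of 6 moves the rate by 16.7 points. Imputed rates are also shown at every visit, and the follow-up windows at Days 86 and 180 are far longer.

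**What to change.** In SAP 7.2.1.1, replace the death condition with wording such as: if a visit is missing and the subject died on or before the last day of that visit's analysis window, that visit and all later visits count as non-response. Deriving the primary as all-organ CR plus PR after the 7.2.2.1 imputation would have the same effect on these deaths and would make the two tables agree by construction. In either case, state the lower and upper day of each analysis window in the SAP.

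The cost is one sentence and a short table of windows. The derivation already exists for the all-organ response, and no new data are needed. The only downside is that the primary rate may fall slightly if such a subject exists.

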6.1.5. Early Termination Visit

An ET visit will be conducted when the following occur:

- In the event that the biopsy results do not confirm GI GVHD, study treatment will be discontinued, and an ET visit will be performed 6 weeks after the last dose of ALXN1007 was received.
- If the subject discontinues for any reason after receiving at least 1 dose of ALXN1007 and before the Day 180 visit, the ET visit should be performed (within 5 days) if possible.

The ET visit assessments will include acute GVHD staging, physical exam, ECG, vital signs, weight, various laboratory tests, PK/PD, antibodies to ALXN1007, exploratory biomarkers, and recording of AEs (see Section 11.2) and concomitant medications and therapies (see Section 8.2).

Note: Subjects must continue antibiotic prophylaxis active against meningococcal infection for 6 weeks after the last dose of ALXN1007.

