13.7.4. Treatment Failures

The proportion of subjects who meet the treatment failure criteria will be summarized at Days 14, 28 and 56 along with 95% CIs. Subjects who discontinue from the study early will be considered treatment failures.

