### **4.1. Changes from Analyses Specified in the Protocol**

Following changes in analyses specified in the protocol are noted:

- Safety analyses will be only performed on safety set as opposed to both safety set and modified safety set as mentioned in the protocol.
- Demographics, baseline characteristics and medical history will be only summarized for safety set as opposed to safety set, modified full analysis set and per-protocol set as mentioned in the protocol.
- The imputation rule has been modified from that described in the protocol for overall acute GVHD response, acute GI-GVHD response and acute GVHD response involving all organs.

In addition due to early termination of the study, an abbreviated CSR will be written and a number of pre-specified analyses will not be performed however by-patient listings will be generated for all data collected for this study.

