#### 5.1.2.4. Treatment Failure

The proportion of treatment failures will be determined over time. The following will be considered as treatment failures:

- No response (all organs)
- Progression (all organs)
- Administration of additional systemic therapy for GVHD (or re-escalation of corticosteroid dose to  $\geq 2.5$  mg/kg/day of prednisone [or methylprednisolone equivalent of 2 mg/kg/day])
- Mortality occurred prior to Day 56

Note: For abbreviated CSR, this endpoint will not be analyzed.

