#### **7.2.1.5. Sensitivity Analyses**

Observed response rates (without any imputation) at Day 28 will be tabulated along with 95% Clopper-Pearson exact confidence intervals. In addition, both imputed and observed results will be presented at all study visits.

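### For living early leavers with no recorded secondary therapy, the SAP carries the last response forward into the Day 28 primary rate where the protocol counts no response, and no planned table applies the protocol rule

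*SAP*

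**What the plan says.** **Protocol rule.** Protocol 13.7.1, on the overall response rate: "Subjects who discontinue from the study early will be imputed as having no response". It sets no condition on earlier response or therapy.

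**SAP rule.** SAP 7.2.1.1 looks first for secondary therapy or death before the missing visit. If either occurred, "all subsequent missing values will be imputed as NR (non-responder), otherwise, last non-missing response will be carried forward".

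**Disclosure.** SAP 4.1 lists the change: "The imputation rule has been modified from that described in the protocol for overall acute GVHD response", along with the GI and all-organ responses. It gives no reason. The same section says that the study ended early, that an abbreviated report will be written, and that by-patient listings will cover all collected data.

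**Sensitivity analysis.** SAP 7.2.1.5: "Observed response rates (without any imputation) at Day 28 will be tabulated along with 95% Clopper-Pearson exact confidence intervals". It does not say whether the denominator is the whole mFAS or only subjects with a Day 28 value.

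**Related endpoints.** Protocol 13.7.2 and 13.7.3 also count early leavers as no response. SAP 7.2.2.1 replaces this with carry-forward and adds: "If first post-baseline response is missing and the patient did not die, no response can be carried forward". For treatment failure, Protocol 13.7.4 says "Subjects who discontinue from the study early will be considered treatment failures", but SAP 5.1.2.4 says "Note: For abbreviated CSR, this endpoint will not be analyzed".

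**Follow-up of leavers.** Protocol 7.3.2 asks subjects who only stop ALXN1007 to keep attending visits through Day 180. Protocol 6.1.5 asks for an early-termination visit within 5 days, where possible, when a subject discontinues before Day 180: "The ET visit assessments will include acute GVHD staging".

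**The concern.** This is an open-label, non-randomised study with no hypothesis test, so the Day 28 rate and its interval are the main efficacy result. The two documents classify one kind of subject in opposite ways: someone who leaves alive, with no recorded secondary therapy and with a response at the last staging. The change favours the drug for such subjects and no reason is given. Results are shown by cohort (SAP 7), and Cohorts 2 and 3 have 3 to about 6 subjects each (Protocol 6.2), so one reclassified subject can visibly move a column. A reader who wants the rate under the protocol rule will find no table that reports it.

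**Working it through.** The documents give no target response rate, dropout rate or power for this endpoint, so there is no stated figure to reproduce. The check compares the rules and then sizes the difference.

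**1. Classification of an mFAS subject with no Day 28 value**

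| Subject | Protocol 13.7.1 | SAP 7.2.1.1 |
|---|---|---|
| Died before the visit | No response (reading death as leaving early) | NR |
| Left alive, secondary therapy recorded | No response | NR |
| Left alive, no secondary therapy, last staging not a response | No response | Non-response carried forward |
| Left alive, no secondary therapy, last staging a response | No response | **Response carried forward** |
| Left alive, no secondary therapy, no post-baseline staging | No response | Not addressed |
| Still in the study, only missed Day 28 | Not addressed | NR after secondary therapy, otherwise last response carried forward |

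Among leavers whom both rules classify, they differ only in the fourth row, and there the SAP gives the more favourable value.

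**2. Size**

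Let N be the mFAS size, r the observed Day 28 responders, m the subjects missing Day 28, and c the subjects in the fourth row. Assume that all m have left or died, that all stay in the denominator, and that no leaver's early-termination staging serves as a Day 28 value.

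- Protocol rule: r/N
- SAP rule: (r + c)/N
- Difference: c/N, which is never negative

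Per affected subject, 1/N is:

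- 1/3 = 33.3 points and 1/6 = 16.7 points (range for Cohorts 2 and 3)
- 1/18 = 5.6 points (Cohort 1 maximum)
- 1/30 = 3.3 points (approximate total in SAP 4)
- 1/36 = 2.8 points (maximum total in Protocol 13.2)

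**3. Illustration with assumed counts: N = 18, r = 9**

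| Analysis | Rate | 95% Clopper-Pearson |
|---|---|---|
| Protocol rule | 9/18 = 50.0% | 26.0 to 74.0 |
| SAP, c = 0 | 9/18 = 50.0% | 26.0 to 74.0 |
| SAP, c = 1 | 10/18 = 55.6% | 30.8 to 78.5 |
| SAP, c = 2 | 11/18 = 61.1% | 35.7 to 82.7 |
| SAP, c = 3 | 12/18 = 66.7% | 41.0 to 86.7 |

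**4. Does the observed-case table supply the protocol figure?**

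That depends on the unstated denominator. With all mFAS subjects it is r/N = 9/18 = 50.0%, equal to the protocol rule under the assumptions in step 2. With only subjects who have data it is r/(N − m): 9/17 = 52.9% (27.8 to 77.0) with one missing, or 9/16 = 56.3% with two missing. Neither of these is the protocol rate.

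**5. Limit of the ordering**

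The order holds for leavers, not for every missing value. Take N = 18, r = 9 and one continuing subject who misses Day 28 and was last staged as NR. The SAP gives 9/18 = 50.0%. Protocol 13.7.1 is silent on this subject, and a protocol analysis that leaves the subject out gives 9/17 = 52.9%, which is higher.

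**The case against.** The case against acting has four parts.

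- **The change is declared.** The protocol leaves analysis detail to the SAP, the study ended early, and no test, error rate or decision threshold is affected. This stands. A reader might infer a concealed change or an inflated rate, but SAP 4.1 lists the change openly and no document shows that anyone is affected. What is missing is a reason and a result under the protocol rule.
- **The affected group is narrow.** Deaths and recorded secondary therapy give NR under the SAP too. Subjects who only stop drug should keep attending. Subjects whose biopsy does not confirm GI GVHD are outside the mFAS. Other leavers should have early-termination staging, and because SAP 7.2.2.1 says that analysis windows are wider than visit windows, that staging may itself fall in the Day 28 window. All this stands, so c may be zero.
- **The figure can be rebuilt.** Listings of all collected data (SAP 4.1), secondary therapies (SAP 7.1.4) and individual staging (SAP 7.2.2.1.1) should allow the protocol rule to be applied by hand. Under the assumptions in the working, observed responders over the mFAS count also give it. So one cannot say that the protocol-rule rate is unrecoverable. The disposition table alone does not settle it, because SAP 7.1.1 splits discontinuations by treatment and follow-up period, not at Day 28.
- **Treatment failure is a different endpoint.** Mixed response is not listed as a failure, so failure is not the complement of response. Dropping it removes a table that would have counted leavers as failures, but that table would not have reported the protocol-rule response rate.

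**Conclusion.** The point holds as a disclosed, unexplained departure on the primary endpoint, with no planned table under the protocol rule. Among leavers with no Day 28 value, the SAP can only raise the rate or leave it unchanged, by 1/N per affected subject: 5.6 points at N = 18 and 16.7 at N = 6. The documents do not give the number affected, and the rates of 55.6% to 66.7% in the working rest on assumed counts. It would go too far to say that the SAP carries every leaver forward, or that its rate must exceed the protocol's: the first ignores the NR rule for death and secondary therapy, and the second fails for continuing subjects who merely miss Day 28. Two smaller gaps also hold: the observed-case denominator is unstated, and SAP 7.2.1.1 does not address a living subject with no post-baseline staging, whom SAP 7.2.2.1 covers only for the GI and all-organ responses.

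**What to change.** Keep the carry-forward result and add one Day 28 sensitivity row beside it, in the mFAS, with all mFAS subjects in the denominator and a Clopper-Pearson interval:

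- A subject with staging in the Day 28 analysis window is classified by that value under the SAP response definition.
- A subject without such a value is a non-responder if he or she discontinued from the study (not merely from ALXN1007) or died before that assessment, or has no post-baseline staging.
- A continuing subject who only misses the Day 28 visit, and has earlier post-baseline staging, is handled by the existing rule in SAP 7.2.1.1.

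The full denominator, the clause on absent staging and the handling of a continuing subject go slightly beyond Protocol 13.7.1. They are there so that every subject has an assigned outcome.

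Also state the denominator of the observed-case table in SAP 7.2.1.5, and give the reason for the imputation change in SAP 4.1.

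The cost is one table row and a few words, with no new data. The row may show a slightly lower rate. If no subject is affected, it will show that the primary result does not depend on the changed rule for leavers.
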